## 9. ADVERSE EVENTS

### 9.1 DEFINITION OF ADVERSE EVENT (AE)

An adverse event is defined as any untoward medical occurrence in a subject participating in a clinical study that does not necessarily have a causal relationship with the pharmaceutical or biological agent under study. An AE can therefore be any of the following:

- Any unfavorable and unintended sign (including laboratory findings), symptom, or disease temporally associated with the use of bermekimab, whether or not it is apparently related to bermekimab;
- A concurrent illness;
- An exacerbation, or an unexpected increase in frequency or intensity of a preexisting condition, including intermittent or episodic conditions.
- A significant or unexpected worsening of the condition/indication under investigation.
- A suspected interaction between the investigational drug and concomitant medications
- Any clinically significant laboratory abnormality (including radiological interpretations, histopathological findings, etc.)

## **9.2 DEFINITION OF SERIOUS ADVERSE EVENT (SAE)**

A serious adverse event is defined as any untoward medical occurrence that meets any of the following criteria:

- Results in death;
- Life-threatening;
- Requires or prolongs inpatient hospitalization;
- Results in a persistent or significant disability;
- An important medical event that, while it may not result in death or be immediately life-threatening or require/prolong hospitalization, may jeopardize the subject and/or may require medical or surgical intervention to prevent one of the outcomes listed above. Examples of such events are intensive treatment in an emergency room or at home for allergic bronchospasm; blood dyscrasias or convulsions that do not result in hospitalization.

Note that seriousness and severity should not be confused. A subject could experience a severe headache that would not qualify as an SAE, while another might experience a mild stroke that, while not severe, would be considered serious.

## **9.3 RECORDING OF ADVERSE EVENTS**

All untoward events occurring between visit 1 and visit 14 (or if subject terminates from study prior to visit 14, seven days after the last administration of bermekimab) on the eCRF, regardless of whether they are considered related to study drug.

All AEs should be recorded in a standard medical terminology as concisely as possible. The AE recorded should not be a procedure or a clinical/laboratory measurement but should reflect the event leading to the procedure or the cause of the clinical/laboratory abnormality, if known. Whenever possible, AEs should be evaluated and recorded as a diagnosis, rather than individual signs and symptoms. However, if a definitive diagnosis is not possible, the individual signs and symptoms should be recorded. Any AE that worsens in intensity, or becomes serious, should be recorded as a new event.

#### **9.4 EVALUATING ADVERSE EVENTS**

All AEs will be graded according to the CTCAE version 4.03.

#### **9.5 ASSESSMENT OF CAUSALITY**

Investigators are required to assess the relationship, if any, of each AE or SAE to the investigational drug using clinical judgment to determine the degree of certainty with which an AE can be attributed to the investigational drug. Alternative causes, such as natural history of the underlying disease, other risk factors, and the temporal relationship of the event to the administration of the study medication must be considered.

Relationship to study drug is summarized as follows:

- **Not Related:** There is another obvious cause of the AE
- **Unlikely to be related:** There is another more likely cause of the AE
- **Possibly related:** The AE could have been due to the investigational drug
- **Probably related:** The AE is probably attributable to the investigational drug
- **Definitely related:** The AE is most likely attributable to the investigational drug

#### **9.6 REPORTING REQUIREMENTS**

Any AE (with the exception of worsening HS symptoms or injection site reactions) of grade 2 or higher must be entered into the eCRF within 24 hours of learning of the event. Any grade 3 or greater injection site reaction must be reported to the sponsor within 24 hours of learning of the event.

All serious adverse events (SAEs) should be reported to the Sponsor within 24 hours of knowledge of the event. These immediate reports should be followed promptly by detailed, written reports. The subject should be followed up until stabilization of the reported SAE, either with full

satisfactory resolution or resolution with sequelae, or until death of the subject. Before declaring the subject is lost to follow-up, three unsuccessful attempts at contact should be made and recorded on the SAE form. The immediate and follow-up reports should identify subjects by unique code numbers assigned to the trial subjects rather than by the subjects' names, personal identification numbers, and/or addresses. The Investigator should also submit SAEs to the IRB/EC according to their IRB/EC guidelines [ICH-GCP E6]. Drug-related Serious Adverse Events will be reported to the FDA by XBiotech's Medical Safety Officer according to 21 CFR 312.32.

## **9.7 REFERENCE SAFETY INFORMATION: POTENTIAL ADVERSE REACTIONS**

831 patients have been treated using bermekimab in patients with advanced solid tumors, advanced hematologic malignancies, metastatic colorectal cancer, peripheral vascular disease, type II diabetes, acne vulgaris, plaque psoriasis, and pyoderma gangrenosum. Over 1200 doses of bermekimab were administered at 7.5 mg/kg to refractory, metastatic CRC patients with cancer associated symptoms at baseline (ECOG performance status 1 and 2). In this trial (PT026), which is the largest controlled trial completed with bermekimab to date (N=309), patients were dosed at 7.5 mg/kg for metastatic colorectal cancer. The most common AEs reported (>10%) were abdominal pain, peripheral edema, fatigue, anemia, constipation, decrease in weight, asthenia, decreased appetite, and nausea. The majority of these events were grade 1 or 2 and appeared to be related to the underlying CRC. The prevalence of these events was similar in the bermekimab and placebo groups. Two infusion reactions were reported in this trial, and they were not serious or severe (grade I or II).

Bermekimab is a recombinant human IgG1 monoclonal antibody specific for human interleukin-1 $\alpha$  (IL-1 $\alpha$ ). As such, it is an immunomodulator that has anti-inflammatory and anti-neoplastic properties. Other agents that could be considered in the same pharmacologic class include biologic agents that target IL-1 receptor antagonist and IL-1 beta. Potential risks for agents in this class include infusion or injection site reactions and risk of infection.

Bermekimab is considered to be a True Human monoclonal antibody. Unlike previous generations of humanized or fully human antibodies, the entire bermekimab heavy and light chain sequences are identical to those found in naturally-occurring human IgG1 $\kappa$ , with the light and heavy chain variable regions being identical to those originally expressed by a peripheral blood B lymphocyte that was obtained from a healthy individual. No *in vitro* affinity maturation or modifications have been made to improve its natural binding affinity (211 +/- 31 pM). We believe that a true human

antibody should be effectively non-immunogenic in humans and thus exhibit optimal activity and pharmacokinetics. To date, no treatment emergent anti-drug antibodies specific to bermekimab have been identified.

The mechanism behind infusion reactions is not clear in all cases. It may involve a reaction against the antibody products themselves, or, against some minor residual component from the manufacturing process (i.e. host cell proteins). To date, there has been a very low incidence of injection site or infusion reactions observed (20 patients out of 831 total; 2.4%). All except two of these patients had grade 1 or 2 reactions that did not result in discontinuation. In order to mitigate this class-specific risk, close monitoring is required during the bermekimab infusion and for at least 1 hour after the end of the infusion. Availability of resuscitation equipment must be ensured. Pre-medication with antihistamines or corticosteroids is not required.

**For the purposes of expedited safety reporting in clinical trials, the following should be considered expected events:**

- Infusion Related Reactions
- Injection Site Reactions

## **10. STATISTICAL PLAN**

This section provides the basis for the statistical analysis plan (SAP) for the study. The SAP may be revised during the study to accommodate amendments to the clinical study protocol, and to make changes to adapt to unexpected issues in study execution and data that may affect planned analyses. Analysis variables are listed in Section 8.

### **10.1 Statistical Hypothesis**

No formal hypothesis tests will be performed for the primary endpoints.

### **10.2 Determination of Sample Size**

The sample size chosen was one of convenience, and no formal sample size calculations were performed.

## 10.3 Analysis Sets

### 10.3.1 Safety Analysis Sets

The safety analysis set (SAF) consists of all patients that receive at least one dose of study medication and will be analyzed as treated.

The secondary endpoints will be analyzed based upon the SAF, as well as the per protocol population (PP). The per protocol population will consist of those patients that complete both the baseline (visit 1) and visit 13 assessments of their hidradenitis (HISCR, PGA, Modified Sartorius, VAS, and DLQI).

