## **2.8 PROHIBITED AND RESTRICTED THERAPIES**

Treatment with certain restricted concomitant medications is allowed once during study to treat acute HS exacerbation, including:

- Systemic therapies with known effectiveness in HS, including corticosteroids, retinoids, or anti-androgen (hormonal) therapies.
- Intralesional/topical steroids
- Laser/light therapies

The use of rescue medications for worsening HS is to be reported in the electronic data capture system. A second flare up of disease and subsequent use of a second rescue therapy for any patient will result in the patient being treated as a non-responder for the purposes of data analysis.

The following concomitant therapies are *prohibited* for the entire duration of the trial:

- Biologics that target IL-1 or TNF-alpha
- Live virus vaccines
- Investigational agents other than bermekimab

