## **3. STUDY DESIGN AND OBJECTIVES**

Phase 2, Open label, multicenter study of two dose cohorts of bermekimab in patients naïve to or having failed prior anti-TNF therapy with moderate to severe Hidradenitis Suppurativa. Bermekimab administered subcutaneously at a dose of 400 mg weekly (13 doses). Patients will be followed for 13 weeks to allow for assessment of safety and preliminary efficacy.

The study protocol will be approved by the Institutional Review Board (IRB) or the Ethics Committee (EC) of the participating study sites. Depending on the participating countries both local and central IRB/EC approvals will be granted. The study will be registered at [www.clinicaltrials.gov](http://www.clinicaltrials.gov) before the enrollment of the first patient. The trial will be conducted in compliance with the protocol, GCP, and all applicable regulatory requirements.

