#### **10.5.3 Analysis of Secondary Endpoints:**

Proportion of patients achieving a positive Hidradenitis Suppurativa Clinical Response (HiSCR) score after 13 weeks will be summarized by treatment group (and pooled overall population). The corresponding 95% confidence interval (CI) for the point estimate will be provided. Subjects previously enrolled in the 200mg/weekly dosing cohort who have received *two or fewer* bermekimab injections (2 x 200mg doses) before beginning the 400mg weekly doses will be included for data analysis together with those receiving all doses at 400mg/weekly. Patients who have received more than 2 bermekimab injections of 200mg may enter the 400mg/week arm; however, only patients who have received *two or fewer* bermekimab injections will be included in the data analysis.

Change in outcomes from baseline to week 13 (VAS for disease, VAS for pain, DLQI, inflammatory lesion count, PGA, Disease Activity Score, and modified Sartorius score) will be summarized using descriptive statistics (n, mean, standard deviation, median, minimum and maximum value). The 95% CI of the mean change from baseline will be provided.

A rank-ordered analysis will be performed for the total abscess and inflammatory nodule count (ranked at 0, 1 or 2) and reduction in pain score (categorized as  $\geq 30\%$  reduction on pain score among patients with baseline score of  $\geq 3$ ). The change in modified Sartorius score will be dichotomized at 4 ( $\leq 4$  least severe disease, higher indicates severe disease). Number and percent under each treatment group (and pooled overall) will be summarized.

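### The per-protocol set in Section 10.3.1 is a five-instrument completer set with no treatment criterion (minor)

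*Combined protocol and SAP*

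**What the plan says.** Section 10.3.1 defines two sets. For the first, "The safety analysis set (SAF) consists of all patients that receive at least one dose of study medication and will be analyzed as treated". For the second, "The per protocol population will consist of those patients that complete both the baseline (visit 1) and visit 13 assessments of their hidradenitis", with the assessments listed as "HISCR, PGA, Modified Sartorius, VAS, and DLQI". The secondary endpoints are analysed on both. HADS and the Disease Activity Score are secondary endpoints in Section 3.1 but are not in that list.

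Three other places link treatment to the analysis or restrict it:

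- Section 2.8 prohibits, among others, "Biologics that target IL-1 or TNF-alpha" throughout the trial and states no analysis consequence. For rescue therapy, a second use "will result in the patient being treated as a non-responder for the purposes of data analysis".
- Section 10.5.3 says "Patients who have received more than 2 bermekimab injections of 200mg may enter the 400mg/week arm", but leaves those patients out of the data analysis.
- Section 5.3 lists the reasons for mandatory discontinuation. Use of a prohibited therapy is not named among them.

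Section 10.5 summarises continuous data on the observations available. No imputation rule is given.

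**The concern.** A per-protocol analysis is normally read as showing the result in patients who were treated as planned. Membership here depends only on data completeness, which has two consequences.

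First, departures from treatment do not affect membership. A patient who skips injections or receives a prohibited biologic is in the set if the visit 1 and visit 13 assessments are complete.

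Second, a gap in one instrument removes the patient from the per-protocol result for every other endpoint. HiSCR is built from lesion counts only (Section 8.2), so a missing DLQI or VAS does not stop HiSCR from being determined, yet it takes the patient out of the per-protocol HiSCR proportion. A missing HADS or Disease Activity Score has no such effect, so the rule is not a consistent completer rule either.

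What is at stake is interpretation. If the safety-set and per-protocol results agree, a reader may conclude that the findings are robust to protocol deviations, and this comparison cannot show that.

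**Working it through.** The plan states no figure to reproduce: Section 10.2 calls the sample size one of convenience. The check is a comparison of passages, followed by two illustrations of size.

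**1. Does any passage add a treatment criterion to the per-protocol set?**

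- Section 2.8, second rescue: this fixes the patient's outcome, not membership.
- Section 2.8, prohibited therapies: no analysis consequence.
- Section 10.5.3, more than two 200 mg injections: this concerns earlier dose level in crossover patients. It sets no minimum number of injections and is not part of the per-protocol definition.
- Section 5.3: does not stop a patient on a prohibited therapy from reaching visit 13.

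None does.

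**2. What does the second analysis add to the first?** For change from baseline, the safety-set analysis of available observations already uses patients with both values for that endpoint. For the listed instruments, the per-protocol analysis is that same analysis minus patients with a gap in another listed instrument. The two differ by data gaps, not by adherence.

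**3. Effect of dropping one patient.** Inputs: n = 10 per group (Synopsis). The illustrative response of r = 6 is the 6 of 10 seen on bermekimab in the earlier placebo-controlled study (Section 1.1).

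- Drop a responder: change = −(n − r)/[n(n − 1)] = −4/90 = −4.4 points, so 6/10 = 60.0% becomes 5/9 = 55.6%.
- Drop a non-responder: change = +r/[n(n − 1)] = +6/90 = +6.7 points, giving 6/9 = 66.7%.
- Pooled, 12/20 = 60.0% becomes 11/19 = 57.9% or 12/19 = 63.2%.

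Exact (Clopper-Pearson) 95% intervals are 26.2–87.8% for 6/10, 21.2–86.3% for 5/9 and 29.9–92.5% for 6/9. The shift is small beside the sampling uncertainty.

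**4. How many patients the rule could drop.** The documents give no missing rate, so m is assumed to be 2%, 5% or 10% per source at visit 13, with sources independent and baseline complete. Share dropped = 1 − (1 − m)^k.

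| m | HiSCR alone (k = 1) | Lesion examination, VAS, DLQI (k = 3) | Five instruments (k = 5) |
|---|---|---|---|
| 2% | 2% | 1 − 0.98³ = 5.9% | 1 − 0.98⁵ = 9.6% |
| 5% | 5% | 1 − 0.95³ = 14.3% | 1 − 0.95⁵ = 22.6% |
| 10% | 10% | 1 − 0.90³ = 27.1% | 1 − 0.90⁵ = 41.0% |

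Of 20 patients, k = 3 means about 1.2, 2.9 or 5.4 lost; k = 5 means 1.9, 4.5 or 8.2; HiSCR alone means 0.4, 1.0 or 2.0. The k = 3 column is more realistic, because HiSCR, PGA and modified Sartorius all draw on counts of nodules, abscesses and fistulas (Section 8.2). All the instruments are also collected in one pre-injection block at visit 13 (Section 5.1), so gaps will tend to occur together. With gaps positively associated in this way, the k = 5 column is an upper bound for five instruments, VAS counted once.

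**The case against.** The case for leaving the text alone has real force.

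- **Nothing valid is lost from the trial.** A reader might infer that a missing DLQI removes the patient from HiSCR altogether. It does not: the secondary endpoints are also analysed on the safety set, where that patient's HiSCR remains. This stands, and it confines the problem to the second analysis.
- **One common denominator is a legitimate choice.** A fixed set lets endpoints be compared in the same patients. That is true, but it justifies a completer set, not the per-protocol label, and the list omits two secondary endpoints.
- **Early stoppers mostly leave the set anyway.** A reader might infer that patients with few injections routinely stay in. Membership requires completed assessments at day 84, no efficacy visits after discontinuation are scheduled, and Section 9.3 ends adverse event recording seven days after the last dose for early terminators. What remains is the patient who misses injections, or takes a prohibited therapy, and still completes visit 13. Nothing in the documents excludes that patient.
- **Treatment rules exist elsewhere.** They do, for second rescue and for crossover patients, but neither enters the per-protocol definition.
- **Further criteria may be in a separate SAP.** Sections 10 and 10.5.5 refer to one. No such criteria appear in the text available, and Section 10 is described as its basis.

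**Conclusion.** The point holds as a minor one. As written, the per-protocol set is a completer set on five named instruments with no treatment criterion. It cannot show the result in patients treated as planned, and it drops valid observations on one endpoint because of gaps in another.

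The reach is limited to the second, descriptive analysis of secondary endpoints in 20 patients. The primary safety analysis is untouched. Section 10.1 plans no formal test of the primary endpoint and Section 10.5.3 describes only summaries and confidence intervals, so no error rate or power is involved.

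Two stronger readings on size are not supported. One is that a single exclusion moves a group's HiSCR by about 10 points. That is the effect of reclassifying one of ten patients; exclusion reaches it only at the extremes (1/10 to 0/9, or 9/10 to 9/9), and at 6/10 the shift is −4.4 or +6.7 points. The other is that 10%, 23% or 41% of patients would be expected to drop out of the set. Those figures need five independent instruments, which the shared lesion counts contradict; about 6%, 14% or 27% is nearer under the same assumed rates. All of these percentages rest on assumed missing rates, and the 60% response is illustrative only.

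**What to change.** Rename the current set *completers* and define it endpoint by endpoint: a patient is included for an endpoint if baseline and visit 13 are both present for that endpoint.

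If a per-protocol set is kept, define it before analysis from data already collected:

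- no therapy prohibited in Section 2.8 before the visit 13 assessment; and
- a minimum share, chosen and stated in advance by the sponsor, of the injections scheduled before that assessment. Visit 13 is assessed before its injection (Section 5.1), so the denominator is the 12 injections at visits 1 to 12, not 13. State whether the one or two 200 mg injections of included crossover patients count.

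Concomitant medications and injections are recorded at the visits (Section 5.2), and Section 10.5.5 already summarises the number of doses. No new data and no change to patient management are needed. The cost is SAP wording and a little programming. The number analysed may differ by endpoint, and the per-protocol number may be slightly smaller.

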## 10.4 Patient Disposition

A listing of all patients prematurely discontinued from the study, along with reasons for discontinuation will be provided. In addition, the total number of patients for each of the following categories will be summarized.

- The total number of screened patients: met the inclusion criteria regarding the target indication and signed the informed consent
- The total number of enrolled patients: met all inclusion/exclusion criteria and receive at least one dose of therapy
- The analysis sets (SAF, PP)
- The total number of patients who discontinued the study, and the reasons for discontinuation
- A listing of patients prematurely discontinued from treatment, along with reasons for discontinuation

## 10.5 Statistical Methods

Continuous data will be summarized for each treatment group using the number of observations available (N), means, standard deviation (SD), minimums, medians, and maximums. Categorical data will be summarized for each treatment group using counts and percentages. Missing data will not be categorized in the summaries.

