### **5.3 DISCONTINUATION OF THERAPY**

If a patient is discontinued from study, the reason for discontinuation must be clearly documented in the source documentation and the EDC.

Study therapy MUST immediately be discontinued for any the following reasons:

- Withdrawal of informed consent (subject's decision to withdraw for any reason)
- Any clinical adverse event, laboratory abnormality, inter-current illness, or clinical progression of disease which, in the opinion of the Principal Investigator, indicates that continued participation in the study is not in the best interest of the subject
- Pregnancy
- Termination of the study by the sponsor
- Imprisonment or the compulsory detention for medical treatment.

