are more than 5 abscesses or draining fistulas. The PGA will be measured on visits 1, 3, 5, 7, 9, 11, 13 and 14.

- Disease Activity Score (baseline to visit 13). This is defined as the sum of scores of all affected areas of each patient. Each area will be evaluated by the following formula: (multiplication of the two largest diameters in each affected area in mm) x (the degree of inflammation of each lesion). This score has been proposed by our study group. The Disease Activity Score will be measured on visits 1, 3, 5, 7, 9, 11, 13 and 14.
- The modified Sartorius score (baseline to visit 13). The Sartorius Scale is used to quantify the severity of HS. Points are awarded for 12 body areas (left and right axillae, left and right sub/inframammary areas, intermammary area, left and right buttocks, left and right inguino-crural folds, perianal area, perineal area, and other): points were awarded for nodules (2 points for each); abscesses (4 points); fistulas (4 points); scars (1 point); other findings (1 point); and longest distance between two lesions (2-6 points, 0 if no lesions); and if lesions are separated by normal skin (yes-0 points; no-6 points). The total Sartorius score is the sum of the 12 regional scores. The modified Sartorius score will be measured on visits 1, 3, 5, 7, 9, 11, 13 and 14.
- Change in AN count (baseline to visit 13). The sum of abscesses and inflammatory nodules for each patient will be measured on visits 1, 3, 5, 7, 9, 11, 13 and 14.
- Change in VAS for Disease Severity and Pain (baseline to visit 13). Patient reported visual analogue scales for pain and disease severity will be measured on visits 1, 3, 5, 7, 9, 11, 13 and 14.
- Change in Dermatology Life Quality Index (DLQI) (baseline to visit 13). This will be measured on visits 1, 3, 5, 7, 9, 11, 13 and 14.
- Change in Hospital Anxiety Depression Scale (HADS) (baseline to visit 13). This will be measured on visits 1, 3, 5, 7, 9, 11, 13 and 14.

Changes in secondary endpoints will be presented by individual cohort, as well as combined across both cohorts.

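### For the change-from-baseline endpoints, the SAF and per-protocol summaries both need a visit-13 value, so their agreement says nothing about dropout

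*Combined protocol and SAP*

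**What the plan says.** The endpoints concerned are the changes from visit 1 to visit 13 in AN count, VAS for disease, VAS for pain, DLQI, HADS, Disease Activity Score, modified Sartorius score and PGA. HiSCR is a responder endpoint and is not part of this point.

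- **Summary rule (section 10.5).** Continuous variables are summarised "using the number of observations available (N), means, standard deviation (SD), minimums, medians, and maximums". The same paragraph adds: "Missing data will not be categorized in the summaries".
- **Change endpoints (section 10.5.3).** These get n, mean, SD, median, minimum and maximum, and then: "The 95% CI of the mean change from baseline will be provided". HADS is not in this list, so only the general rule in section 10.5 covers it.
- **Analysis sets (section 10.3.1).** Secondary endpoints are analysed on the SAF (everyone who received at least one dose) and on PP. For PP: "The per protocol population will consist of those patients that complete both the baseline (visit 1) and visit 13 assessments of their hidradenitis", with HiSCR, PGA, modified Sartorius, VAS and DLQI named.
- **Stopping (section 5.3).** The grounds include adverse events and worsening disease: "clinical progression of disease which, in the opinion of the Principal Investigator, indicates that continued participation in the study is not in the best interest".
- **Data collected (section 8.2).** For AN count: "The sum of abscesses and inflammatory nodules for each patient will be measured on visits 1, 3, 5, 7, 9, 11, 13 and 14". The other scales follow the same visits.

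Sections 5.1 and 5.2 schedule no efficacy assessment at early termination.

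**The concern.** Offering both SAF and PP suggests that one analysis keeps everyone treated and the other keeps the completers, so that a reader can compare them to judge the effect of dropout. For a change score to visit 13 that comparison is nearly empty, because the requirement that defines PP is also what a patient needs to enter the SAF summary.

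The plan also lists worsening disease and adverse events as grounds for stopping. Patients who leave on those grounds may well be doing worse than those who stay, and there is no control arm in which similar losses could offset the effect. Section 1.2 presents the study as groundwork for later randomised trials, so a mean change that is too favourable could be carried into their planning. The assessments at visits 3, 5, 7, 9 and 11 show how such patients were doing before they left, but the visit-13 summaries do not use them.

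**Working it through.** **Inputs.** Planned n is 20, as 10 in Group A plus 10 in Group B (synopsis). Section 10.2 calls this a convenience sample. It gives no SD, correlation or dropout rate, so the plan has no figure of its own to reproduce, and the dropout inputs below are assumptions.

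**1. Who contributes.**

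| Patient | SAF change summary | PP |
|---|---|---|
| All named visit-13 assessments done | in | in |
| Visit-13 value for this endpoint, another named assessment missing | in | out |
| No visit-13 value (for example, stopped earlier) | out | out |

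Only the middle row separates the two sets. Patients who stopped early and were not assessed at visit 13 are in the last row.

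**2. Size of the shift.** With d of n patients missing, the observed mean differs from the all-treated mean by

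(d/n) × (completers' mean − dropouts' mean).

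If dropouts are given zero change, the observed mean is n/(n − d) times the all-treated mean:

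- Pooled, n = 20: 20/18 = 1.11 for d = 2; 20/16 = 1.25 for d = 4.
- Per group, n = 10: 10/9 = 1.11 for d = 1; 10/8 = 1.25 for d = 2.

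Other values for the dropouts, pooled, with the completers' gain set to 1:

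- They keep half the gain: 1/[(18 + 2 × 0.5)/20] = 1/0.95 = 1.05 for d = 2; 1/[(16 + 4 × 0.5)/20] = 1/0.90 = 1.11 for d = 4.
- They worsen by half the gain: 1/[(18 − 2 × 0.5)/20] = 1/0.85 = 1.18 for d = 2; 1/[(16 − 4 × 0.5)/20] = 1/0.70 = 1.43 for d = 4.

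**3. Simulated dropout after a poor visit.** Both simulations used n = 20, correlation 0.8 between successive assessments and 4,000 trials per dropout level. They differ in how strongly a poor visit leads to leaving.

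| Dropout | Bias, stronger link (SD) | Bias, weaker link (SD) | 95% CI coverage, weaker link |
|---|---|---|---|
| 10% | 0.13 | 0.10 | 93% |
| 20% | 0.24 | 0.18 | 89% |
| 30% | 0.35 | 0.27 | 82% |

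The bias is in the favourable direction. The 95% CI half-width is about 0.5 SD, so 0.13 SD is about a quarter of it and 0.24 SD about half.

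A likelihood estimate that uses the earlier visits had bias below 0.01 SD. Its standard error was 9% to 25% larger under the stronger link and 5% to 17% larger under the weaker one. Root-mean-square error under the stronger link:

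- 10% dropout: √(0.219² + 0.131²) = 0.255 SD observed-case, against 0.238 SD.
- 20% dropout: √(0.222² + 0.242²) = 0.328 SD observed-case, against 0.260 SD.

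**4. Limiting cases (20,000 runs, n = 20).**

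- Missingness unrelated to outcome: bias about 0, coverage about 95%.
- Exactly the worst patients missing: bias 0.18 SD with 84% coverage for d = 2; 0.33 SD with 62% coverage for d = 4.
- Exactly the best patients missing: the bias has the same size and the opposite sign.

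**The case against.** **The bias is conditional.** A reader might infer that the planned results will overstate improvement. The documents do not support that. They give no dropout rate, and loss unrelated to outcome causes no bias. Progression is one of several grounds for stopping and rests on the investigator's judgement. Section 2.8 also allows restricted medication once for an exacerbation. A second rescue leads to non-responder status with no stated withdrawal, so some worsening patients may stay and be measured. All of this stands. That rule, however, supplies no value for a continuous score.

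**The loss is visible.** A reader might infer that patients vanish unnoticed. They do not. Sections 10.5 and 10.5.3 print n, and section 10.4 requires SAF and PP counts, discontinuation totals and listings with reasons. This stands, but disclosure does not correct the mean or its interval.

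**These are not the only results.** A reader might take the mean changes to be the trial's whole efficacy result. HiSCR is also reported with a 95% CI, and section 10.5.3 adds categorised AN, pain and Sartorius summaries. The primary endpoint is safety, and section 10.1 plans no formal test of it.

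**The plan is silent rather than wrong.** The phrase on available observations is one item in a general list, and section 10 describes itself as the basis for an SAP that may be revised. A rule could still be added, but none is in the documents. Followed as written, the plan gives the result described here.

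**The simulation suits the model.** Patients left after an observed poor visit, which is the missing-at-random condition that a likelihood estimate needs. Efficacy is assessed every two weeks with no early-termination assessment, so the worsening that prompts a patient to leave may never be recorded, and the model would not recover it. The simulated estimator was also a sequential regression rather than the exact model proposed below. This stands, and it is why the model should not be the only addition.

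**Conclusion.** The point holds in conditional form. For these endpoints the SAF summary is in effect a visit-13 observed-case analysis. It cannot count patients who stopped before visit 13, and comparing it with PP says nothing about dropout.

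Whether the mean change is actually too favourable depends on why patients leave. With assumed outcome-related dropout the bias is about 0.10 to 0.13 SD at 10% and 0.18 to 0.24 SD at 20%. With unrelated dropout it is about zero. These figures rest on n = 20, a correlation of 0.8 and dropout driven by an earlier poor visit, none of which can be checked against the documents apart from n. The consequence is limited to descriptive secondary results and their confidence intervals; the safety objective is unaffected. The change is worth making before analysis because the data it needs are already scheduled.

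**What to change.** In section 10.5.3:

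- **Keep** the observed-case summary, and print n at every assessment visit.
- **Add (a), on the SAF:** an analysis that assigns zero change to patients who stopped for progression or an adverse event before visit 13. State that other missing values stay missing in this analysis.
- **Add (b), on the SAF:** a repeated-measures likelihood estimate of the visit-13 mean change with 95% CI, by group and pooled, using visits 3, 5, 7, 9, 11 and 13. Include visit, group, visit-by-group and baseline terms. The visit-by-group term is needed so that the visit-13 group means are not forced to a constant difference. With 20 patients, use a structured covariance such as heterogeneous AR(1).
- **PGA:** it is a six-level ordinal scale, so summarise it by category and count patients who stopped as not improved.
- **Wording:** name HADS in the list. Give the time point as visit 13 (day 84), because section 10.5.3 says week 13 and day 91 is visit 14.

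The cost is SAP text and one model for each of the seven continuous endpoints, with no new visits or data. Analysis (b) assumes missing at random and gives somewhat wider intervals. Zero change in (a) is a conventional value that may be too harsh or too lenient. The two should therefore be read together, beside the observed-case result.
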